## **INTRODUCTION**

Dental caries is the most common chronic disease of childhood. According to the American Academy of Pediatric Dentistry, it is estimated that 5% of children under the age of 6 experience severe early childhood caries, an additional 15% roughly 1.5 million US children experience lesser levels of ECC, a condition that may necessitate restorative dental treatment. Prefabricated crowns are the treatment of choice for children with rampant caries involving large or multiple surface lesions or developmental defects. In such situations, crowns reinforce the tooth and provide increased durability and longevity over intracoronal restorations such as fillings. Crowns also reduce the chance of recurrent caries. 

In routine clinical practice, preformed metal crowns, also known as stainless steel crowns (SSC) are frequently indicated due to their durability, relatively low cost, and minimal technique sensitivity. They are adapted to the prepared tooth and cemented with a biocompatible luting agent. According to American Academy of Pediatric Dentistry, use of SSCs should be considered in patients at high risk for caries, whose cooperation is affected by age, behavior or medical history. Such patients frequently receive treatment under sedation or general anesthesia.

Although SSCs are highly effective, esthetics can be a concern for parents. Prefabricated zirconia crowns provide an esthetic solution and are now available for both primary incisors and molars. Zirconium dioxide (zirconia) is a crystalline solid that has strength similar to metals while its color is similar to that of teeth. According to a recent randomized controlled trial, both stainless steel and zirconia crowns proved to be an excellent choice for posterior full coverage restoration of primary teeth. However, zirconia crowns have shown to have better performance with regards to esthetics, gingival response and plaque retention.

The process of preparing the tooth for a prefabricated zirconia crown requires a circumferential subgingival preparation. Prefabricated zirconia crown preparations include occlusal reduction of 1-2 mm followed by supragingival reduction of 0.5-1.25 mm circumferentially. Once prepared, caries is removed, and the preparation is reduced 1-2 mm subgingivally to create a feather edge margin. Tissue irritation and bleeding is inherent in this process. If hemostasis is inadequate when the crown is cemented, blood contamination will affect the integrity of the tooth-cement-crown interface. Zirconia crowns are also translucent, and blood incorporated into the cement may cause visible discoloration, resulting in poor esthetics.

Hemostasis can be achieved by allowing the tissues to clot naturally using direct pressure with gauze. However, in clinical settings, it is not always possible or desirable to wait for extended periods of time. Thus, clinicians have relied upon topical or injected vasoconstrictors such as epinephrine to facilitate rapid hemostasis. Epinephrine is a powerful stimulator of both alpha and beta-adrenergic receptors, eliciting different effects depending on the tissue involved. Alpha-adrenergic receptors predominate in tissues such as oral mucosa and periodontium where epinephrine causes vasoconstriction of blood vessels. Beta 1 receptors, predominantly located in the heart, can increase heart rate and contraction force. Beta 2 receptors are predominately located in the lungs and skeletal muscle. Activation can cause bronchodilation in lungs, vasodilation of skeletal muscle and increased cardiac output. In medical and dental surgical practice, dilute formulations of injectable epinephrine are used to provide local hemostasis; however, when injected, they may raise serum epinephrine levels and increase potential for cardiopulmonary side effects. In contrast, topical epinephrine causes local vasoconstriction of the contacted mucosa, resulting in decreased systemic absorption. Administration of topical epinephrine has been shown

to result in elevation of serum concentrations 140-times less than injections of even dilute epinephrine preparations.

Topical epinephrine has been used widely in medicine and dentistry to achieve rapid hemostasis. Studies by Korkmaz et al and Gunaratane et al showed no significant hypertensive episodes and no hemodynamic parameter changes associated with placement of 1:1000 topical epinephrine. However, others have reported topical epinephrine sensitivity on only small portion of patients. These studies showed that topical epinephrine may induce significant hemodynamic changes in only a subset of patients which included the ones with preexisting cardiovascular diseases.

A literature review of prior studies investigating the effects of topical racemic epinephrine showed its effectiveness to decrease intraoperative bleeding. Degerliyurt K. et al. showed practical use of topical epinephrine without safety concerns for sinus surgery. Vickers et al. studied the cardiovascular effects of topical epinephrine pellets and 20% ferric sulfate in endodontic surgery. They found that neither agent had any statistically significant cardiovascular effects. However, subjectively, epinephrine pellets showed better hemostasis outcome than 20% ferric sulfate.

Complications associated with use of topical epinephrine are extremely rare, and changes in cardiovascular outcomes have not been shown to be statistically significant. To the best of our knowledge, no well-designed clinical trials have been conducted to assess the cardiovascular effects of topical epinephrine on gingival tissue in a pediatric population.

The overarching purpose of this split-mouth randomized pilot study was to determine the efficacy and safety of receiving treatment with topical racemic epinephrine compared to placebo, measured by cardiovascular and hemostasis outcomes. Specifically, the primary objective of this

study was to determine if the use of racemic epinephrine has any effect on heart rate, blood pressure, or cardiac rhythm in children receiving dental care under general anesthesia. We hypothesized that the use of topical racemic epinephrine would be associated with no significant change on heart rate, blood pressure, or mean arterial pressure in children receiving dental care under general anesthesia compared to patients receiving a placebo.

The secondary objective of this study was to determine if the use of racemic epinephrine has any effect on hemostasis, as measured subjectively by the dentist performing the procedure. We hypothesized that the use of topical racemic epinephrine would reduce clotting time around the gingival tissue, resulting in more rapid hemostasis.

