## METHODS

The study was approved by the Institutional Review Board at the University of Washington (STUDY00006670). Participants and their parents/legal guardian were recruited from a pool of patients who were scheduled to receive comprehensive dental care under general anesthesia (GA) at the University of Washington Center for Pediatric Dentistry. Families were approached regarding study participation the day of the initial dental surgery consultation or were contacted by phone at least 2 days prior to their scheduled dental surgery appointment. Consent was obtained the day of the surgery. Inclusion criteria included American Academy of Anesthesiologists physical status classification (ASA) I or II, English speaking, and having caries lesions requiring prefabricated crowns on both primary maxillary first molars, teeth #B and I.

Subjects were excluded from the study if the parents or guardians were not able to communicate with the study coordinator in English or the patient had severe systemic illness (ASA III or greater), cardiac arrhythmia, cardiovascular disease, diabetes, thyroid disease and/or prescribed anti-arrhythmic, antihypertensive, or ionotropic medications. Subjects were also excluded if they required pulpotomy or pulpectomy treatment on the primary maxillary first molars.

This was a single blinded, split-mouth randomized controlled pilot study. We recruited patients from June 2019 until November 2019. Sixteen children met inclusion criteria and were approached for participation. Three patients were excluded from the study: One patient did not meet the inclusion criteria after new radiographs were taken under GA and two caregivers declined to participate in the study on the day of surgery (Figure 1).

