After successful intubation, necessary radiographs were taken, a throat pack was placed, followed by cleaning, dental examination and treatment planning. Next, the maxillary first primary molar that was randomized to be completed first was prepared to receive a zirconia crown. To reduce pressure stimulation, no dental isolation (e.g. rubber dam) was used during any of the study procedures. After preparation, an appropriately sized zirconia crown was fit, and baseline heart rate and blood pressure were recorded. Next, two saline or intervention pellets were stretched and applied directly around the gingival tissue of the prepared tooth covering the tooth circumference. Control pellets were prepared by soaking in 0.9% sodium chloride (physiological saline) whereas intervention pellets were obtained directly from the manufacturer, containing an average of 0.55 mg (0.42 to 0.68 mg/pellet) of racemic epinephrine hydrochloride per pellet (HemeRx, Racellet#3, Sprig Oral Health Technologies, Inc. Loomis, CA). Pellets were maintained in position for one

minute with gauze pressure based on manufacturer's recommendation. After pellet removal, any residual coagulum was removed using suction or moistened gauze.

Cardiovascular outcomes including patient's systolic blood pressure (SBP), diastolic blood pressure (DBP) and heart rate (HR) and mean arterial pressure (MAP) were recorded via standard automatic noninvasive arterial cuff immediately before pellet placement (baseline) and again at 1, 2, 3, 4 and 5 minutes after placement.

The adequacy of hemostasis was determined subjectively by the operating dentist/principal investigator ([name]), as "adequate" or "inadequate" at baseline and again at 1, 2, 3, 4 and 5 minutes after placement. Adequate hemostasis was defined as cessation of blood flow from gingival tissue. Inadequate hemostasis was defined as continued blow flow from gingival tissue, with blood contamination of the prepared tooth. Figures 2 and 3 demonstrate examples of adequate vs. inadequate hemostasis. Figure 4 demonstrates pre and post-op intraoral photos of maxillary arch of one of the patients.

Following study procedures, the remainder of each patient's dental care was completed, including application of rubber dam isolation, sealants, composite restorations, pulpotomies, stainless-steel crowns and extractions. All patients were discharged on the same day after adequate recovery and observation time.

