Data was analyzed using Stata SE version 14.2 (College Station, TX) software. Descriptive statistics are reported as mean and standard deviation. Paired t-test and one-way repeated analysis of variance (ANOVA) were used for comparison of cardiovascular outcomes within controls (Table 1) and within interventions (Table 2). A paired t-test with equal variance was used for comparing control and intervention cardiovascular values as well as time to hemostasis adequacy (Table 3). McNemar's Exact test was used to compare whether a patient reached adequate

hemostasis in the intervention and control sides. A p-value < 0.05 was considered to be statistically significant.

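### The primary hypothesis predicts no significant cardiovascular change, but the methods text names no confidence interval for the paired difference, and non-significance in about 13 pairs would not exclude an effect

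*Combined protocol and SAP*

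**What the plan says.** The Introduction gives the primary objective as "to determine if the use of racemic epinephrine has any effect on heart rate, blood pressure, or cardiac rhythm" in children having dental care under general anesthesia. The hypothesis that follows takes a no-change form: epinephrine "would be associated with no significant change on heart rate, blood pressure, or mean arterial pressure" relative to placebo. Safety is part of the study's overall purpose.

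The Methods section records SBP, DBP, HR and MAP "immediately before pellet placement (baseline) and again at 1, 2, 3, 4 and 5 minutes after placement". Its closing statistical paragraph names these elements for the cardiovascular outcomes:

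- description: "Descriptive statistics are reported as mean and standard deviation";
- within each condition: paired t-test and one-way repeated-measures ANOVA (Tables 1 and 2);
- between conditions: "A paired t-test with equal variance was used for comparing control and intervention cardiovascular values" (Table 3);
- threshold: "A p-value < 0.05 was considered to be statistically significant".

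The text names no confidence interval, margin, target effect, power or planned sample size. On numbers, the Methods say "Sixteen children met inclusion criteria and were approached for participation" and "Three patients were excluded from the study". The study is described as a pilot.

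**The concern.** A hypothesis of no significant change, analysed only with tests for a difference, can be supported by one kind of result: p ≥ 0.05. That result becomes more likely as the data become fewer or noisier, so on its own it does not show which effects are absent. Here the question is the primary cardiovascular one, in anesthetised children. The useful product of a small pilot is an estimate with its uncertainty, and the methods text does not name one.

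Means and SDs may not fill the gap. If they are given per side, a reader cannot rebuild the interval for the paired difference, because that also depends on the within-patient correlation, which is not among the listed summaries.

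**Working it through.** The plan gives no sample-size, power or margin figure, so there is nothing of its own to reproduce first.

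**Inputs**
- Pairs: 16 approached − 3 excluded = 13. The number is derived; the text does not state it.
- Test: two-sided paired t-test at 0.05, df = 12. This is assumed, because the description mixes paired and two-sample terms and gives no sidedness.
- SD of the paired difference: not given, so results are in SD units. The values 5, 10 and 15 (bpm or mmHg) are illustrative assumptions.
- Correlations between outcomes and minutes: not given; 0, 0.5 and 0.8 are assumed, equal for every pair of comparisons.

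**Precision.** Half-width = t(0.975, 12) × SD / √13 = 2.179 × SD / 3.606 = 0.604 SD. For SDs of 5, 10 and 15 this is 3.0, 6.0 and 9.1 units. A non-significant mean difference lies within 0.604 SD of zero, so its interval can reach almost 2 × 0.604 = 1.21 SD.

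**Power of one comparison** (noncentral t)
- 80% power needs a true shift of 0.847 SD. With 12 to 16 pairs this moves only from 0.89 to 0.75 SD.
- At a true shift of 0.5 SD, power is 38.2%, so the result is non-significant 61.8% of the time. At 1.0 SD it is non-significant 8.9% of the time.

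**Several comparisons.** The hypothesis covers four parameters, and there are five post-placement times, so 4 × 5 = 20 possible comparisons. The Methods do not say which times are tested. The table gives the chance that all comparisons are non-significant.

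| True shift 0.5 SD in | Correlation 0 | 0.5 | 0.8 |
|---|---|---|---|
| all four parameters, one comparison each | 15% | 30% | 42% |
| one of the four only | 53% | 55% | 57% |
| all 20 parameter-by-minute comparisons | about 0.01% | 8% | 26% |

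The independent case can be checked directly: 0.618⁴ = 0.146, and 0.618²⁰ is below 0.0001. The other entries are simulated.

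**Rebuilding the interval from per-side SDs.** With equal SDs on both sides, SD of the difference = √(2(1 − r)) × SD per side. The half-width is therefore 1.414 × 0.604 = 0.85 SD at r = 0 and 0.632 × 0.604 = 0.38 SD at r = 0.8. It more than halves on a quantity the reader would not have.

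**The case against.** The strongest reply is that there is no mismatch. The objective asks about any effect, which a difference test addresses, and the hypothesis can be read literally as a forecast of the test result. That stands as far as the objective goes. A reader might infer that the plan treats p ≥ 0.05 as proof of safety, but the documents do not say this. The point is limited to what the named analysis could support.

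Second, Tables 1 to 3 may already carry intervals. This also stands: the absence is established for the methods text only. If Table 3 gives intervals for the paired differences, what remains is mainly how the conclusion is drawn.

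Third, a reader might take 62% as the chance of a falsely reassuring study. The documents do not support that. It applies to one comparison at a 0.5 SD shift. Over all 20 the corresponding figure runs from about 0.01% to 26% with a uniform shift, and it is higher if only one parameter moves. The overall risk is not established in either direction.

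Fourth, a reader might conclude that 13 pairs are uninformative. That is not shown, because no SD and no relevant effect size are stated. At an assumed SD of 5, a non-significant result keeps its 95% interval within about 2 × 3.0 = 6 units of zero.

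Fifth, pilot status lowers any expectation of confirmatory evidence of no effect. True, and it is why an estimate with an interval is asked for rather than an equivalence test.

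**Conclusion.** The point holds as a cheap improvement of moderate severity. Followed as written, the methods text allows the no-change hypothesis to be supported only by non-significance, which does not exclude an effect, and it names no interval to show what is excluded.

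Confidence is high on two things: what the methods text names, and the SD-unit figures for one comparison (half-width 0.60 SD, 0.85 SD for 80% power, 62% missed at 0.5 SD). These rest on 13 derived pairs and a two-sided paired t-test. Everything in bpm or mmHg, and everything across several comparisons, rests on assumed SDs and correlations. An error of inference in the documents, a wrong test for the objective, and a lack of intervals in the tables are not established.

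**What to change.** In the statistical paragraph of the Methods:

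1. For HR, SBP, DBP and MAP, report the within-patient epinephrine-minus-saline difference at each of minutes 1 to 5 with its 95% confidence interval, taking account of the pre-placement baseline already recorded.
2. If simple change scores are used for this, say that they can cost precision. With equal variances, the SD is multiplied by √(2(1 − ρ)), where ρ is the correlation between the baseline and later paired differences. The interval widens when ρ is below 0.5, and at ρ = 0.2 it is √1.6 = 1.26 times as wide (about 26% wider).
3. Base the cardiovascular conclusion on the effect sizes the intervals do and do not exclude, and state that p ≥ 0.05 is not taken as evidence of no effect.
4. Leave the hypothesis in the Introduction as it stands. The text is in the past tense, so label any analysis added after data were seen as post hoc.

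The cost is some wording and 20 intervals from measurements already made, with no new patients. There are two downsides. The conclusion may be that the data are inconclusive. And the 20 intervals are unadjusted: with no true effect, at least one excludes zero about 64%, 44% or 24% of the time at assumed correlations of 0, 0.5 or 0.8 (1 − 0.95²⁰ = 0.64 for independence). They should be read for the sizes they exclude, not by counting those that miss zero.

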## METHODS

The study was approved by the Institutional Review Board at the University of Washington (STUDY00006670). Participants and their parents/legal guardian were recruited from a pool of patients who were scheduled to receive comprehensive dental care under general anesthesia (GA) at the University of Washington Center for Pediatric Dentistry. Families were approached regarding study participation the day of the initial dental surgery consultation or were contacted by phone at least 2 days prior to their scheduled dental surgery appointment. Consent was obtained the day of the surgery. Inclusion criteria included American Academy of Anesthesiologists physical status classification (ASA) I or II, English speaking, and having caries lesions requiring prefabricated crowns on both primary maxillary first molars, teeth #B and I.

Subjects were excluded from the study if the parents or guardians were not able to communicate with the study coordinator in English or the patient had severe systemic illness (ASA III or greater), cardiac arrhythmia, cardiovascular disease, diabetes, thyroid disease and/or prescribed anti-arrhythmic, antihypertensive, or ionotropic medications. Subjects were also excluded if they required pulpotomy or pulpectomy treatment on the primary maxillary first molars.

This was a single blinded, split-mouth randomized controlled pilot study. We recruited patients from June 2019 until November 2019. Sixteen children met inclusion criteria and were approached for participation. Three patients were excluded from the study: One patient did not meet the inclusion criteria after new radiographs were taken under GA and two caregivers declined to participate in the study on the day of surgery (Figure 1).

Randomization was performed in two stages. Using Stata 14.2 (StataCorp, College Station, TX) statistical software we first randomized whether the control treatment would be applied to the primary right or left maxillary first molar. The first randomization resulted in assignment of the right side of the mouth for the control treatment. This assignment was maintained for all participants. The second randomization step determined the treatment sequence; whether control or intervention treatment was done first. A randomization list was created and placed into a password protected Excel file prior to the start of the study. The order in which the patient received the intervention (either first or second) was randomly assigned to each patient using the randomization list.

The main objective of this method was to have each patient serve as their own control and ensure randomization of the timing (first or second) of the experimental condition. Parents were not present during the procedure, and patients were unconscious and therefore blinded to the intervention. The treating dentist and study personnel were not blinded.

Each patient's weight and medical history was updated on the day of surgery. All patients fasted for at least eight hours prior to the procedure. They were transferred to the operating room and received mask inhalation induction (8% sevoflurane and 50-70% N2O/O2). Monitoring

equipment was applied after the patient was anesthetized, and it was maintained in place throughout the course of the procedure. Vital sign measurements included capnography, oxygensaturated hemoglobin percentage (SpO2), heart rate (HR) in beats per minute (bpm), and cardiac rhythm-which was continuously recorded from a 5-lead electrocardiogram (ECG). The systolic blood pressures (SBP) and diastolic blood pressures (DBP) were measured in millimeters of mercury (mmHg) via standard automatic noninvasive arterial cuff on the ankle or upper arm.

All baseline vitals were recorded and peripheral intravenous (IV) access was obtained. Patients then received 1 to 2mg/kg of propofol, Decadron 4 to 6mg total and 0.5 mg/kg of ketorolac via IV, followed by direct laryngoscopy and nasotracheal intubation. Anesthesia was maintained throughout the procedure with a continuous IV infusion of propofol (50-100 mcg/kg/min), Remifentanil infusion (0.05-0.1 mcg/kg/min), and inhaled nitrous oxide/oxygen (30-70%).

After successful intubation, necessary radiographs were taken, a throat pack was placed, followed by cleaning, dental examination and treatment planning. Next, the maxillary first primary molar that was randomized to be completed first was prepared to receive a zirconia crown. To reduce pressure stimulation, no dental isolation (e.g. rubber dam) was used during any of the study procedures. After preparation, an appropriately sized zirconia crown was fit, and baseline heart rate and blood pressure were recorded. Next, two saline or intervention pellets were stretched and applied directly around the gingival tissue of the prepared tooth covering the tooth circumference. Control pellets were prepared by soaking in 0.9% sodium chloride (physiological saline) whereas intervention pellets were obtained directly from the manufacturer, containing an average of 0.55 mg (0.42 to 0.68 mg/pellet) of racemic epinephrine hydrochloride per pellet (HemeRx, Racellet#3, Sprig Oral Health Technologies, Inc. Loomis, CA). Pellets were maintained in position for one

minute with gauze pressure based on manufacturer's recommendation. After pellet removal, any residual coagulum was removed using suction or moistened gauze.

Cardiovascular outcomes including patient's systolic blood pressure (SBP), diastolic blood pressure (DBP) and heart rate (HR) and mean arterial pressure (MAP) were recorded via standard automatic noninvasive arterial cuff immediately before pellet placement (baseline) and again at 1, 2, 3, 4 and 5 minutes after placement.

The adequacy of hemostasis was determined subjectively by the operating dentist/principal investigator ([name]), as "adequate" or "inadequate" at baseline and again at 1, 2, 3, 4 and 5 minutes after placement. Adequate hemostasis was defined as cessation of blood flow from gingival tissue. Inadequate hemostasis was defined as continued blow flow from gingival tissue, with blood contamination of the prepared tooth. Figures 2 and 3 demonstrate examples of adequate vs. inadequate hemostasis. Figure 4 demonstrates pre and post-op intraoral photos of maxillary arch of one of the patients.

Following study procedures, the remainder of each patient's dental care was completed, including application of rubber dam isolation, sealants, composite restorations, pulpotomies, stainless-steel crowns and extractions. All patients were discharged on the same day after adequate recovery and observation time.

Data was analyzed using Stata SE version 14.2 (College Station, TX) software. Descriptive statistics are reported as mean and standard deviation. Paired t-test and one-way repeated analysis of variance (ANOVA) were used for comparison of cardiovascular outcomes within controls (Table 1) and within interventions (Table 2). A paired t-test with equal variance was used for comparing control and intervention cardiovascular values as well as time to hemostasis adequacy (Table 3). McNemar's Exact test was used to compare whether a patient reached adequate

hemostasis in the intervention and control sides. A p-value < 0.05 was considered to be statistically significant.

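### Side was drawn once for the whole trial (saline always right, epinephrine always left), so a left-right difference arising after pellet placement cannot be separated from the drug effect on hemostasis

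*Combined protocol and SAP*

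**What the plan says.** All of this is in the METHODS section of the combined protocol and SAP, except the hypothesis, which is in the INTRODUCTION.

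- **Side.** At the first stage, "we first randomized whether the control treatment would be applied to the primary right or left maxillary first molar". The outcome was: "The first randomization resulted in assignment of the right side of the mouth for the control treatment. This assignment was maintained for all participants". The study teeth are #B and #I, one on each side, so epinephrine was always on the left.
- **Order.** The second stage worked patient by patient: "The order in which the patient received the intervention (either first or second) was randomly assigned to each patient using the randomization list".
- **Blinding.** "The treating dentist and study personnel were not blinded".
- **Outcome.** The operating dentist gave each prepared tooth a subjective two-level grade for hemostasis. The text on timing and definition reads: "at baseline and again at 1, 2, 3, 4 and 5 minutes after placement. Adequate hemostasis was defined as cessation of blood flow".
- **Analysis.** "A paired t-test with equal variance was used for comparing control and intervention cardiovascular values as well as time to hemostasis adequacy (Table 3"). For the binary outcome, "McNemar's Exact test was used to compare whether a patient reached adequate" hemostasis on the intervention and control sides. The analysis paragraph describes neither a side term nor a baseline adjustment.
- **Hypothesis.** "We hypothesized that the use of topical racemic epinephrine would reduce clotting time around the gingival tissue, resulting in more rapid hemostasis".

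**The concern.** A split-mouth design removes differences between children. It removes differences between the two sides of the mouth only if each treatment appears on both sides across the sample. Here it does not: treatment and side are the same variable.

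That matters for hemostasis because the outcome is local. Between placement and grading, the dentist presses gauze by hand and clears coagulum by suction or gauze, then grades by eye, knowing the treatment. Access or pressure could differ between right and left. If so, the difference would be read as a drug effect, or would hide one.

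What is at stake is the secondary hypothesis of faster hemostasis. A difference in either hemostasis test could come from the drug, from side, or from both. Recruiting more patients under the same scheme would not shrink the bias; it would only estimate the mixture more precisely.

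**Working it through.** The plan states no sample-size or power figure, so there is nothing of its own to reproduce.

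**Inputs.** From METHODS: 16 approached less 3 excluded gives 13 pairs (assuming all are analysed), and significance is at 0.05 (taken as two-sided). Every left-right difference below is an assumption, because the documents give none. The drug effect is set to zero throughout.

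**1. Can the effects be separated?** Take four kinds of row: right and left, each at baseline and after placement.

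- Post-placement rows only: intercept, side and treatment have rank 2 of 3.
- With baseline rows: intercept, side, post and treatment have rank 4 of 4. A side difference that is constant over time could therefore be estimated in a longitudinal model.
- Adding a post-placement side term (side x post) gives rank 4 of 5, because that column is identical to treatment.
- With 13 patient effects plus treatment, side and order, using one post-placement outcome per tooth, the rank is 15 of 16. Order is estimable; side and treatment are not separately estimable. If side is allocated per patient, the rank is 16 of 16.

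**2. Paired t-test, normal differences.** The noncentrality is d x sqrt(13), where d is the side shift in SDs of the paired difference. There are 12 degrees of freedom and the critical t is 2.179.

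| d | noncentrality | rejection at nominal 5% |
|---|---|---|
| 0.1 | 0.36 | 6.3% |
| 0.25 | 0.90 | 13.2% |
| 0.5 | 1.80 | 38.2% |
| 0.75 | 2.70 | 70.0% |

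**3. Paired t-test on the trial's 1-5 minute grid.** The chance of reaching adequacy in each minute is 30% on the right, with the sides independent.

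| left, per minute | never adequate scored 6 | complete pairs only |
|---|---|---|
| 30% | 5.1% | 5.1% |
| 35% | 7.1% | 5.0% |
| 40% | 12.2% | 6.6% |
| 50% | 30.0% | 13.7% |

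(20,000 and 4,000 simulated trials per cell, respectively.)

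**4. McNemar's exact test.** With independent sides, the discordant probabilities are pL(1 - pR) and pR(1 - pL). Rejection is summed exactly over all splits of 13 pairs.

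| right v left adequate | rejection |
|---|---|
| 50% v 50% | 1.5% |
| 50% v 60% | 2.8% |
| 50% v 65% | 4.6% |
| 50% v 66% | 5.1% |
| 50% v 70% | 7.5% |
| 30% v 70% | 34.1% |

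**5. How much can the baseline grades show?** A baseline McNemar test needs at least 6 discordant pairs, all one way: 2 x 0.5^6 = 0.031, whereas 5 pairs give 0.0625. If baseline adequacy were 5% on one side and 20% on the other, the test would find it 1.7% of the time.

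**6. Does per-patient side allocation cure it?** Simulated with 13 patients, blocks of 4 and 8, 20,000 runs and no drug effect. The paired difference with side and period terms rejects 4.7% to 5.0% for side shifts up to 0.75 SD combined with period shifts up to 1 SD, with bias about zero. McNemar's test with 30% base adequacy and side gaps of 0, 20 and 40 points rejects 1.3%, 1.1% and 0.8%.

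**The case against.** The strongest reply is that nothing in the documents suggests a left-right difference. The teeth are matching molars in the same child, prepared alike, with the same pellets, pressure time and assessor. Side was set by a random draw, not picked to favour the drug; order was randomised; and the fixed side is openly disclosed. The study is a pilot, and only a secondary outcome is touched.

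Much of this stands as a limit on severity: the size of any side effect is unknown. It does not restore identifiability. One draw gives only two possible side allocations, mirror images of each other, while the tests treat the 13 pairs as if side had been allocated 13 times. Randomised order deals with period effects only. Disclosing the scheme is not the same as stating its consequence for the hemostasis result.

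The illustrations also need care, because they do not form one scenario. The grid case of 30% v 50% per minute implies adequacy by 5 minutes of 1 - 0.7^5 = 83% v 1 - 0.5^5 = 97%. There McNemar's test rejects only 0.9%, and the shift in time (never adequate scored 6) is about 0.44 SD. The 0.5 and 0.75 SD rows therefore go beyond that model, and the binary test is much less exposed within it.

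A further point widens the concern. A difference in bleeding severity before placement, with both sides graded inadequate, is also inseparable from the drug in the two planned tests. The INTRODUCTION calls bleeding inherent in the preparation, so the baseline grades may be nearly all inadequate and tell little.

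Finally, the documents contain no results or discussion text, so a side limitation may already be stated where hemostasis is reported.

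**Conclusion.** The concern holds. Treatment and side are completely aliased for hemostasis after placement, and neither pairing, randomised order nor the described tests separates them. This follows from the allocation rule and needs no assumption. The practical impact does rest on assumptions: there may be no side difference at all. If there is one, the t-test on time to adequacy is the more exposed test (13.2% false positives at 0.25 SD, 38.2% at 0.5 SD). McNemar's test is conservative at 13 pairs and, from a 50% base, exceeds 5% only for gaps above about 15 points. Heart rate and blood pressure are not affected if side has no systemic effect. It should be fixed, as a limitation on a secondary outcome.

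**What to change.** **Completed data.** No reanalysis can remove the aliasing.

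- Where the hemostasis result is reported, say that it is confounded with tooth side, and do not present it as a purely randomised drug effect.
- Report the paired counts of baseline adequacy by side as a partial check, as counts and not as a p-value.
- Label any side-adjusted analysis using the baseline grades as assuming a side difference that is constant over time.

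The cost is one sentence and one small table from data already collected.

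**Follow-on trial.**

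- In the pre-generated list, randomise side as well as order for each patient (four cells: epinephrine left or right, first or second).
- Use varying block sizes, for example 4 and 8, and conceal the allocation, because the dentist and staff are unblinded. The list already sits in a password-protected file; what needs adding is who may open it and when.
- Analyse the paired difference in time to adequacy with terms for side and period. McNemar's exact test stays valid for the binary outcome once side is randomised.

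The cost is one more column in the list, no extra patients or procedures, and two residual degrees of freedom. At 13 pairs that is 10 instead of 12, with a critical t of 2.23 instead of 2.18.
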